7.1.1 Temporary Discontinuation

It may be necessary for a participant to temporarily discontinue study drug, which will be managed by the Investigator on a case-by-case basis.

7.1.2 Rechallenge

It may be necessary for a participant to restart the study drug after temporarily discontinuation, which will be managed by the Investigator on a case-by-case basis.

7.2 Participant Discontinuation/Withdrawal from the Study

A participant may withdraw from the study at any time at his/her own request or may be withdrawn at any time at the discretion of the Investigator for safety, behavioral, or compliance, positive COVID-19 test or suspected SARS-CoV-2 infection, or administrative reasons. This is expected to be uncommon.

At the time of discontinuing from the study, if possible, an early discontinuation visit should be conducted, as shown in the schedule of activities (SoA; [Section 1.3](#)). See SoA for data to be collected at the time of study discontinuation and follow-up and for any further evaluations that need to be completed.

The participant will be permanently discontinued from the study drug and the study at that time.

If the participant withdraws consent for disclosure of future information, the Sponsor may retain and continue to use any data collected before such a withdrawal of consent.

If a participant withdraws from the study, he/she may request destruction of any samples taken and not tested, and the Investigator must document this in the study site study records.

Participants who voluntarily withdraw are termed dropouts. Dropouts and participants withdrawn due to protocol violations may be replaced following discussion with the Principal Investigator and Sponsor.

Participants withdrawn due to an AE will not be replaced. Subjects who have withdrawn from the study cannot be re-randomized (treated). Their subject and randomization numbers must not be reused.

7.3 Lost to Follow-up

A participant will be considered lost to follow-up if he/she repeatedly fails to return for scheduled visits and is unable to be contacted by the study site.

The following actions must be taken if a participant fails to return to the clinic for a required study visit:

- The study site must attempt to contact the participant and reschedule the missed visit as soon as possible, counsel the participant on the importance of maintaining the assigned visit schedule and ascertain whether the participant wishes to and/or should continue in the study.
- Before a participant is deemed lost to follow-up, the Investigator or designee must make every effort to regain contact with the participant (where possible, via telephone calls, and if necessary, a certified letter to the participant's last known mailing address or local

equivalent methods). These contact attempts should be documented in the participant's study record.

- Should the participant continue to be unreachable, he/she will be considered to have withdrawn from the study.
- Study site personnel, or an independent third party, will attempt to collect the vital status of the participant within legal and ethical boundaries for all participants randomized, including those who did not get study drug. Public sources may be searched for vital status information. If vital status is determined as deceased, this will be documented, and the participant will not be considered lost to follow-up. Sponsor personnel will not be involved in any attempts to collect vital status information.

8.0 STUDY ASSESSMENTS AND PROCEDURES

Study procedures and their timing are summarized in the SoA ([Section 1.3](#)). Protocol waivers or exemptions are not allowed.

Immediate safety concerns should be discussed with the Sponsor immediately upon occurrence or awareness to determine if the participant should continue or discontinue study drug.

Adherence to the study design requirements, including those specified in the SoA ([Section 1.3](#)), is essential and required for study conduct.

All screening evaluations must be completed and reviewed to confirm that potential participants meet all eligibility criteria. The Investigator will maintain a screening log to record details of all participants screened and to confirm eligibility or record reasons for screening failure, as applicable.

Safety results that could unblind the study will not be reported to study sites or other blinded personnel until the study has been unblinded.

8.1 Efficacy Assessments

Participants will score their symptoms as per the United States Food and Drug Administration 2018 guidelines (see [Section 10.4](#)), on a scale from zero to 3, where:

- 0 = absent symptoms (no sign/symptom evident)
- 1 = mild symptoms (sign/symptom present, but minimal awareness; easily tolerated)
- 2 = moderate symptoms (definite awareness of sign/symptom that is bothersome but tolerable)
- 3 = severe symptoms (sign/symptom that is hard to tolerate; causes interference with activities of daily living [ADL] and/or sleeping)

The symptoms to be evaluated are rhinorrhea, sneezing, nasal itching, nasal congestion, red/burning eyes, tearing, itchy/watery eyes, and itching of ears/palate or throat.

Composite scores will be determined as per the following:

- Total nasal symptoms score (TNSS-3): the sum of rhinorrhea, sneezing, and nasal itching scores (maximum 9).
- Total ocular symptoms score (TOSS): the sum of red/burning eyes, tearing, itchy/watery eyes scores (maximum 9).

- Total symptoms score (TSS): the sum of rhinorrhea, sneezing, nasal itching, and nasal congestion; red/burning eyes, tearing, and itchy/watery eyes; and itching of ears/palate or throat scores (maximum 27).

8.2 Safety Assessments

The Principal Investigator and staff must register and assess the following variables: AEs, SAEs, AEs leading to discontinuation, and AESIs.

Symptoms assessed for efficacy (including changes in severity): rhinorrhea, sneezing, nasal itching, nasal congestion, red/burning eyes, tearing, itchy/watery eyes, and itching of ears/palate or throat to be considered as AEs as per Investigator's clinical judgment.

8.2.1 Physical Examinations

Physical examination includes at a minimum: head and neck examination, heart and respiratory auscultation; peripheral lymph nodes and abdomen examination.

8.2.2 Nasal Examination

Nasal examination will be performed as follows:

- External inspection: skin changes (eg, skin lesions/ erythema), deformity.
- Internal inspection: nasal mucosa inspection for any abnormalities, nasal cavities alignment:
 - Nasal vestibule: skin changes (eg, ulceration)/ swelling/ asymmetry,
 - Nasal septum: polyps/deviation,
 - Inferior turbinates: asymmetry/inflammation/ polyps.
- Palpation of nasal bones and cartilage for:
 - Alignment,
 - Tenderness or irregularity (if suspicious of fracture in trauma).
- Nasal airflow assessment

8.2.3 Vital Signs

Vital signs include oral body temperature, heart rate, respiratory rate, systolic and diastolic blood pressure. Heart rate, respiratory rate, systolic and diastolic blood pressure will be measured after at least 3 minutes in sitting position.

Vital sign assessments will consist of 1 pulse and 1 blood pressure measurement.

8.2.4 Electrocardiograms

Electrocardiograms will be performed if deemed necessary, as per the Investigator's discretion.

8.2.5 Clinical Safety Laboratory Tests

Routine clinical laboratory testing will be conducted if deemed necessary, as per the Investigator's discretion. A rapid antigen test will be performed before EEU entry, for SARS-CoV-2 infection.

If laboratory values from non-protocol-specified laboratory tests performed at the institution's local laboratory require a change in participant management or are considered clinically significant by the Investigator (eg, SAE or AE or dose modification), then the results must be recorded.

8.2.6 Pregnancy Testing

Women of childbearing potential should only be included after a confirmed menstrual period and a negative highly sensitive urine pregnancy test.

Additional pregnancy testing is not required for this study.

8.3 Adverse Events, Serious Adverse Events, and Other Safety Reporting

The definitions of AEs and SAEs can be found in [Section 10.2](#).

Adverse events will be reported by the participant (or, when appropriate, by a caregiver, surrogate, or the participant's legally authorized representative).

The Investigator and any qualified designees are responsible for detecting, documenting, and recording events that meet the definition of an AE or SAE and remain responsible for following up all SAEs, AEs related to study drug, or AEs that lead to discontinuation from the drug or study (see [Section 7.0](#)).

The method of recording, evaluating, and assessing causality of AEs and SAEs and the procedures for completing and transmitting SAE reports are provided in [Section 10.2](#).

8.3.1 Time Period and Frequency for Collecting Adverse Event and Serious Adverse Event Information

All AEs and SAEs will be collected from the signing of the informed consent form (ICF) until EOS, at the time points specified in the SoA ([Section 1.3](#)).

Medical occurrences that begin before the start of study drug but after obtaining informed consent will be recorded as medical history/current medical conditions, not as AEs.

All SAEs will be recorded and reported to the Sponsor or designee immediately and under no circumstance should this exceed 24 hours of the Investigator's awareness of the event, as indicated in [Section 10.2](#) and [Section 10.3](#). The Investigator will submit any updated SAE data to the Sponsor or designee within 24 hours of their awareness of the updated information.

Investigators are not obligated to actively seek information on AEs or SAEs after conclusion of the study participation. However, if the Investigator learns of any SAE, including a death, at any time after a participant has been discharged from the study, and he/she considers the event/cause of death to be reasonably related to the study drug or study participation, the Investigator must promptly notify the Sponsor or designee.

The method of recording, evaluating, and assessing causality of AE and SAE and the procedures for completing and transmitting safety reports are provided in [Section 10.2](#) and [Section 10.3](#).

8.3.2 Method of Detecting Adverse Events and Serious Adverse Events

Care will be taken not to introduce bias when detecting AEs and/or SAEs. Open-ended and nonleading verbal questioning of the participant is the preferred method to inquire about AE occurrences.

8.3.3 Follow-up of Adverse Events and Serious Adverse Events

After the initial AE/SAE report, the Investigator is required to proactively follow each participant at subsequent visits/contacts. All SAEs and AESIs (as defined in [Section 8.3.6](#)) will be followed via a follow-up phone call with the participant until 7 days after Visit 5 for AEs and 30 days after Visit 5 for both SAEs and AESIs. Further information on follow-up procedures is provided in [Section 10.2](#) and [Section 10.3](#).

8.3.4 Regulatory Reporting Requirements for SAEs

Prompt notification by the Investigator to the Sponsor of an SAE is essential so that legal obligations and ethical responsibilities toward the safety of participants and the safety of a study drug under clinical investigation are met.

The Sponsor has a legal responsibility to notify both the local regulatory authority and other regulatory agencies about the safety of a study drug under clinical investigation. The Sponsor will comply with country-specific regulatory requirements relating to safety reporting to the regulatory authority, European Union Eudravigilance Database (as applicable), Institutional Review Boards (IRBs)/ Independent Ethics Committee (IECs), and Investigators.

An Investigator who receives an Investigator safety report describing an SAE or other specific safety information (eg, summary or listing of SAEs) from the Sponsor will review and then

file it along with the IB and will notify the IRB/IEC, if appropriate according to local requirements.

Investigator safety reports must be prepared for suspected unexpected serious adverse reactions (SUSARs) and unanticipated adverse device events according to local regulatory requirements and Sponsor policy and forwarded to Investigators as necessary.

8.3.5 Pregnancy

Details of all pregnancies in female participants and, if indicated, female partners of male participants will be collected after the start of study drug and until 4 days after D5.

If a pregnancy is reported, the Investigator will record pregnancy information on the appropriate form and submit it to the Sponsor or designee within 24 hours of learning of the female participant or female partner of male participant (after obtaining the necessary signed informed consent from the female partner) pregnancy and should follow the procedures outlined in [Section 10.3](#).

While pregnancy itself is not considered to be an AE or SAE, any pregnancy complication (or elective termination) of a pregnancy for medical reasons will be reported as an AE or SAE.

If the outcome of the pregnancy meets the criteria for immediate classification as an SAE (ie, spontaneous abortion, stillbirth, neonatal death, or congenital anomaly [including that in an aborted fetus, stillbirth, or neonatal death]) the Investigator will report according to the SAE reporting procedures described in [Section 10.3](#).

The participant/pregnant female partner will be followed to determine the outcome of the pregnancy. The Investigator will collect follow-up information on the participant/pregnant female partner and the neonate and the information will be forwarded to the Sponsor or designee.

Any post-study pregnancy-related SAE considered reasonably related to the study drug by the Investigator will be reported to the Sponsor as described in [Section 8.3.4](#). While the Investigator is not obligated to actively seek this information in former study participants/pregnant female partner, he or she may learn of an SAE through spontaneous reporting.

Any female participant who becomes pregnant while participating in the study will discontinue study drug or be withdrawn from the study.

Prior to continuation of study drug following pregnancy, the following must occur:

- The Sponsor and the relevant IRB/IEC give written approval.
- The participant gives signed informed consent.

- The Investigator agrees to monitor the outcome of the pregnancy and the status of the participant and her offspring.

8.3.6 Adverse Events of Special Interest

An AESI is an AE (serious or nonserious) of scientific and medical concern specific to the Sponsor's product or program, for which ongoing monitoring and immediate notification by the Investigator to the Sponsor is required. Such events may require further investigation in order to characterize and understand them. Adverse events of special interest may be added, modified or removed during a study by protocol amendment.

Specific AESI(s) for this study include systemic hypersensitivity reactions with manifestations such as angioedema, chest tightness, dyspnea, flushing, and systemic anaphylaxis. Subjects with this diagnosis from Investigator during treatment period are to be advised to avoid use of fexofenadine in the future.

8.3.7 Treatment Satisfaction and Recommendation

The participant's satisfaction of the efficacy of this pre-treatment approach (comparing active drug versus placebo group) will be recorded using a 4-point Numerical Rating Scale:

- 1 = very satisfied
- 2 = satisfied
- 3 = dissatisfied
- 4 = very dissatisfied.

The participant's intention of recommending the pre-treatment approach will be either 'yes' or 'no'.

8.4 Pharmacokinetics

Pharmacokinetic parameters are not evaluated in this study.

8.5 Pharmacodynamics

Pharmacodynamic parameters are not evaluated in this study.

8.6 Genetics

Genetics are not evaluated in this study.

8.7 Biomarkers

Biomarkers are not evaluated in this study.

8.8 Immunogenicity Assessments

Immunogenicity is not evaluated in this study.

8.9 Health Economics

Health economics parameters are not evaluated in this study.

9.0 STATISTICAL CONSIDERATIONS

The SAP will be finalized prior to database lock, and it will include a more technical and detailed description of the statistical analyses described in this section. This section is a summary of the planned statistical analyses of the most important endpoints including primary and key secondary endpoints.

9.1 Statistical Hypotheses

In order to evaluate the additional benefit in term of efficacy of 2 days pre-treatment before the allergen exposure, the mean area under the plasma concentration-time curve (AUC) of TNSS-3 will be compared between Arm A and Arm B at V4, the following statistical null hypothesis and alternative will be tested:

- $H_0: AUC_{0-6} \text{ TNSS-3 of A} = AUC_{0-6} \text{ TNSS-3 of B}$
- $H_1: AUC_{0-6} \text{ TNSS-3 of A} \neq AUC_{0-6} \text{ TNSS-3 of B}$

The study will be positive if the null hypothesis (H_0) is rejected, and the active pre-treatment leads to lowering the symptoms compared to placebo.

9.1.1 Multiplicity Adjustment

The following multiplicity testing procedures will be used to control the type I error:

- The secondary efficacy endpoints will be tested only if the primary endpoint is significant.
- The multiplicity of secondary efficacy endpoints will be handled using Hochberg's step-up test.
- For the other secondary efficacy endpoints and the exploratory efficacy endpoints, p-values will be provided for descriptive purpose only.
- The number of AEs defined as other secondary endpoint will be analyzed only with descriptive statistics (no p-value will be provided).

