9.3.2 Primary Endpoint Analysis

All efficacy endpoints analysis will be performed on the mITT population.

The primary analysis will be the comparison of the primary efficacy endpoint (ie, AUC of the TNSS-3 from H0 to H6) between Arm A and Arm B, using an analysis of covariance (ANCOVA) with treatment group as fixed effect and the baseline value of TNSS-3 (ie, at H0 at V4) as covariate. This primary analysis will be conducted on mITT analysis population.

Table 4 Efficacy Analyses

Endpoint	Statistical Analysis Methods
Primary The AUC of the TNSS-3 from H0 to H6 at V4.	The primary analysis will be the comparison of AUC of the TNSS-3 from H0 to H6 between the Arm A and Arm B, using ANCOVA with treatment group as fixed effect and the baseline value of TNSS-3 (ie, at H0 at V4) as covariate.
Secondary 
 • AUC of TOSS from H0 to H6 at V4 • AUC of TNSS-3 from H0 to H12 at V4 • AUC of TOSS from H0 to H12 at V4 • AUC of TNSS-3 from randomization (D1) to V4 (D4) • AUC of TOSS from randomization (D1) to V4 (D4) • Safety: Frequency of AEs 	All secondary endpoints based on the AUC (ie, TSS and TOSS) will be analyzed using an ANCOVA model, with treatment group as fixed effect and the baseline values as covariate. The TNSS-3, TOSS, and TSS will be analyzed using MMRM, with treatment, time point and treatment group by time point interaction as fixed effect with their respective H0 scores as baseline covariate. The TNSS-3, TOSS, TSS, and individual symptom score by time point will be analyzed given the mean and 95% CI. Incidence of treatment-emergent adverse events will be presented in counts and percentages.
Exploratory 
 •  	The AUC (ie, TSS and TOSS) will be analyzed using ANCOVA of the exploratory endpoints, with treatment group as fixed effect and the baseline values as covariate. The analysis of exploratory endpoints will be conducted on mITT analysis population.

Abbreviations: AE = adverse event, ANCOVA = analysis of covariance, AUC = area under the plasma concentration-time curve, CI = confidence interval, D = day, H = hour, mITT = modified intent-to-treat, MMRM = Mixed Models for Repeated Measures, TNSS-3 = Total Nasal Symptoms Score of 3 symptoms, TOSS = Total Ocular Symptoms Score, TSS = Total Systems Score, V = visit.

Note: A 2-sided alpha-niveau of 5% will be applied for the primary endpoint. Additionally, a 5% significance niveau will be applied for the Hochberg approach.

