9.5 Sample Size Determination

Number of subjects (N) = 96 randomized participants (86 evaluable participants)

All eligible participants will be randomized into 1 out of 2 Arms with the randomization ratio allocation 1:1 as follows:

- Arm A: two days of pre-treatment with fexofenadine, then fexofenadine 180 mg during the test pollen challenge.
- Arm B: two days of pre-treatment with placebo, then fexofenadine 180 mg during the test pollen challenge.

The primary efficacy endpoint is the AUC of TNSS-3 (including rhinorrhea, sneezing, and nasal itching, where each symptom is scored from 0 to 3) from H0 to H6 at Visit 4. The maximum score of TNSS-3 is 9.²

The expected benefit of the pre-treatment or the variability of the pre-treatment using the AUC of the TNSS-3 were not published in the literature when the pre-treatment with fexofenadine before allergen exposure has been evaluated.²⁰ Therefore, given the previous study LPS15332 using TNSS-3, the mean (SD) of the AUC_{h2-h12} of the TNSS-3 has been estimated to be equal to 26.34 (16.66) on the placebo group and 18.53 (13.73) on the fexofenadine group after 3 hours of pollen exposure in the period 3, thus a common SD, estimated to be equal to 15, has been used for the sample size calculation.¹⁴ An MCID is commonly defined as a 0.55 change on Total Nasal Symptoms Score of 4 symptoms (TNSS-4) when 4 individual symptoms (ie, rhinorrhea, nasal congestion, nasal itching, and sneezing) are measured.¹⁶

Assuming a common SD=15 and a targeted effect size of 0.70 for the primary endpoint, it will correspond to a difference of AUC of TNSS-3 between Arm A and Arm B of 10.5, which may be interpreted as a difference of TNSS-3 around 2 points between 2 Arms at each time point (which is higher than the MCID of TNSS-3 with 3 individual symptoms). Therefore, at least 86 evaluable patients in both, Arm A and B (ie, included in the mITT population, meaning 43 patients in each arm) are needed to detect a 0.70 effect size for the additional benefit of two days of pre-treatment with fexofenadine on the SAR symptoms with 90% of power and a 2-sided type I error of 5%, using a 2-sample t-test which is assumed to be roughly equivalent

to the primary analysis that will be planned. This sample size has been calculated using EAST6.5 software.

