6.6. Statistical Tests

The default significant level will be (5%); CIs (confidence intervals) will be 95% and all tests will be two-sided, unless otherwise specified in the description of the analyses.

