16.2.1. Secondary Efficacy Variables & Derivations

The TOSS is a composite score calculated as the sum of red/burning eyes, tearing, itchy/watery eyes scores (maximum 9). The individual scores are collected in e-diary. The AUC will be computed using the linear trapezoidal method (22) for all the variables below. The mean score and its 95% CI will be plotted across respective timepoints. This plot will also include the LS mean and 95% CI of the AUC.

- AUC of TOSS from H0 to H6 at V4
- AUC of TNSS-3 from H0 to H12 at V4
- AUC of TOSS from H0 to H12 at V4
- AUC of TNSS-3 from randomization (D1) to V4 (D4)
- AUC of TOSS from randomization (D1) to V4 (D4)

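### Secondary AUC endpoints: Hommel's procedure would be a free but small improvement on the planned Hochberg step-up

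*Protocol*

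**What the plan says.** Protocol 9.1.1 sets a gate: "The secondary efficacy endpoints will be tested only if the primary endpoint is significant". Behind it, "The multiplicity of secondary efficacy endpoints will be handled using Hochberg"'s step-up test. SAP 7.5 repeats both rules.

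The note under Protocol Table 4 gives the levels: "A 2-sided alpha-niveau of 5% will be applied for the primary endpoint", and "a 5% significance niveau will be applied for the Hochberg approach". The note does not give sidedness for the Hochberg tests, but SAP 6.6 does: "all tests will be two-sided, unless otherwise specified in the description of the analyses".

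Table 4 and SAP 16.2.1 list the same five secondary AUC endpoints:
- TOSS from H0 to H6
- TNSS-3 from H0 to H12
- TOSS from H0 to H12
- TNSS-3 from D1 to D4
- TOSS from D1 to D4

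Adverse events, also listed as secondary in Table 4, are descriptive only. Protocol 9.1.1 adds: "For the other secondary efficacy endpoints and the exploratory efficacy endpoints, p-values will be provided for descriptive purpose only". Neither multiplicity section says which endpoints those other ones are. Neither document gives a reason for choosing Hochberg or states power for the secondary endpoints.

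**The concern.** Hommel's procedure is the full closed test built on Simes tests of every intersection of hypotheses. Hochberg's step-up is a conservative shortcut to that test and needs the same dependence condition. A plan that accepts Hochberg has therefore already accepted what Hommel requires. With five p-values and software to compute the adjustment, the simplicity of the shortcut is worth little.

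What is at stake is the secondary claims. The secondary objective covers nasal and ocular symptoms, and no ocular endpoint is primary, so a confirmatory ocular claim can come only through this family. The sample size was set for the primary endpoint alone. Three of the five AUCs are measured on the challenge day. The other two start at randomization and run up to V4, in a study held outside the ragweed season, so weaker effects on those two are plausible. A mix of moderate and weak p-values is a pattern in which the two procedures can disagree.

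**Working it through.** **1. The plan's own sample size.** Protocol 9.5 gives the inputs: "Assuming a common SD=15 and a targeted effect size of 0.70 for the primary endpoint", 90% power, two-sided 5%. By the normal approximation, n per arm = 2(1.960 + 1.282)² / 0.70² = 42.9, so 43 per arm and 86 in total. Allowing for 10% dropout, 86 / 0.90 = 95.6, so 96. Both stated figures reproduce. (The exact t-test gives 43.87, so 44 per arm; its power at 43 is 89.4%.) The simulations below use 43 per arm.

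**2. The two rules.** Order m p-values as p(1) ≤ … ≤ p(m), with α = 0.05.
- Hochberg: find the largest i with p(i) ≤ α/(m − i + 1), and reject hypotheses 1 to i.
- Hommel: find the largest j with p(m − j + k) > kα/j for every k = 1,…,j, and reject every hypothesis with p ≤ α/j. If there is no such j, reject all.

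Both reject all m only when p(m) ≤ 0.05, so the chance of claiming all five is identical. For m = 2 the rules coincide.

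**3. A worked example:** p = 0.012, 0.018, 0.030, 0.40, 0.60.
- Hochberg compares these with 0.010, 0.0125, 0.0167, 0.025 and 0.05. Every p-value exceeds its limit, so there is no claim. Adjusted p-values: 0.060, 0.072, 0.090, 0.60, 0.60.
- Hommel: j = 5 fails because 0.018 is not above 2(0.05)/5 = 0.020. j = 4 holds: 0.018 > 0.0125, 0.030 > 0.025, 0.40 > 0.0375, 0.60 > 0.05. Reject p ≤ 0.05/4 = 0.0125, which gives one claim. Adjusted p-values: 0.048, 0.060, 0.090, 0.60, 0.60.

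A second case, p = 0.003, 0.015, 0.027, 0.029, 0.052, gives one rejection with Hochberg and two with Hommel.

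**4. How often it matters.** The documents give no effects or correlations for the secondary endpoints, so these are assumptions: effects from 0 to 0.7 SD and correlations from 0 to 0.95. Each scenario has 400,000 simulated trials, with the primary tested first and then five secondary tests. Selected rows (percentages of all trials, except the last column, which is the one before it divided by the gate pass rate):

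| Assumed effects (SD) | Correlation | Pass gate | ≥1 claim, Hochberg | ≥1 claim, Hommel | Gain (points) | Results differ | Differ, given gate |
|---|---|---|---|---|---|---|---|
| All 0.70 | 0.5 | 90.06 | 88.35 | 88.57 | 0.22 | 0.96 | 1.1 |
| Primary 0.70; secondaries 0.6, 0.6, 0.5, 0.2, 0.2 | 0 | 90.03 | 81.59 | 82.22 | 0.63 | 2.05 | 2.3 |
| Same | 0.8 | 90.13 | 69.05 | 70.03 | 0.98 | 1.90 | 2.1 |
| All 0.5 | 0 | 63.92 | 59.11 | 59.64 | 0.53 | 2.29 | 3.6 |
| All 0.5 | 0.8 | 64.20 | 55.02 | 56.05 | 1.03 | 2.21 | 3.4 |
| All 0.3 | 0.8 | 28.50 | 19.30 | 20.03 | 0.73 | 1.44 | 5.1 |

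Over the whole grid of 36 scenarios:
- The gain in power for at least one claim is 0.0 to 1.0 points.
- Results differ in 0.03% to 2.3% of all trials.
- At most 0.03 extra claims per trial are expected.
- Hommel never lost a Hochberg rejection.
- Secondary-family error was at most 4.4% with either procedure.

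A separate set of scenarios assumed 0.35–0.65 SD on the three V4 AUCs, 0–0.3 SD on the two D1–V4 AUCs, and correlations of 0.4–0.85 among the V4 AUCs. It gave gains of 0.8 to 1.3 points, with an additional claim in 1.9% to 3.1% of trials that pass the gate.

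**5. Size of the family.** With three endpoints the results differed in only 0.2% to 0.6% of trials. With two they never differ. In four scenarios with weak or null D1–V4 effects, restricting the family to the three V4 AUCs changed Hochberg power for at least one claim by about 3 to 7 points.

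**The case against.** The strongest reply is that nothing is broken. Hochberg is valid, pre-specified and stated the same way in both documents. Trial success rests on the primary endpoint alone, and neither error control nor sample size changes. That stands: this is a refinement.

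A reader might infer that the plan throws away secondary claims on a material scale. The figures do not support that. With every effect at the planned 0.70 and correlation 0.5, the gain is 0.22 points. The worked example was picked to show a move from no claim to one, which the power figures put at roughly 1% of trials or fewer. Conditional figures climb to 5.1% in the row with all effects at 0.3 SD, but only 28.5% of such trials reach the secondary tests.

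A reader might also take the five-endpoint family as settled. It is inferred from the endpoint lists. Protocol 9.0 speaks of key secondary endpoints and 9.1.1 of other secondary endpoints. The objectives table of Protocol 3.0 is absent from the public copy and may have drawn the line. This objection also stands, and step 5 shows that naming the family matters more than the choice of procedure.

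It does not stand that the change would need a protocol amendment, with the approvals in Protocol 10.1.1. SAP 3.3 says the SAP supersedes the protocol's statistical methods.

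**Conclusion.** The point holds as an optional improvement. Hommel needs no assumption beyond those Hochberg already needs, cannot lose a rejection and sometimes adds one. With a five-endpoint family the gain is about 0 to 1.3 percentage points of power for at least one secondary claim. The results differ in up to about 3% of trials that pass the gate, and in somewhat more if all true effects are 0.5 SD or less. These sizes rest wholly on assumed effects and correlations, so the benefit in this trial cannot be pinned down. The direction does not depend on them. The documents do not support calling Hochberg an error or the loss substantial.

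**What to change.** Before unblinding, amend SAP 7.5 in two ways:
- State that the tested family is the five AUC endpoints listed in SAP 16.2.1, if that is the intent.
- Replace Hochberg's step-up with Hommel's procedure at two-sided 5% and report Hommel-adjusted p-values.

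Record both in SAP 3.3 as changes from Protocol 9.1.1 and the Table 4 note. The primary gate, alpha, endpoints and the 86/96 sample size are untouched. The cost is a short SAP edit and a changed option in the multiplicity program. If the blind has already been broken, keep Hochberg as pre-specified.
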